### VITAL SIGNS

Descriptive statistics for vital sign parameters (i.e. diastolic and systolic blood pressure, pulse, respiration rate, body temperature, and weight) and changes from baseline will be presented by visit and treatment group.

### ELECTROCARDIOGRAMS

Descriptive statistics for ECG parameters and changes from baseline will be presented by visit and treatment group. ECG interpretation (categorized as normal; abnormal, not clinically

significant; and abnormal, clinically significant) will be presented by visit and treatment group using frequency count.

## **OTHER SAFETY ANALYSES**

Results from Doppler sonography and platelet function tests will be presented.

### **9.7.1.9 Other Analyses**

## **HEALTH ECONOMIC ANALYSES**

The health outcome economics, as measured by healthcare resources utilization, will be summarized by item and by treatment group. The categorical variables will be tested using CMH, Chi-squared or Fisher's exact test, while continuous variables may be analyzed by t-test or Wilcoxon rank sum test as appropriate.

Details of these analyses will be provided in a separate analysis plan.

## **9.7.2 Determination of Sample Size**

The proposed sample size is based on comparisons of the primary efficacy variable, with the response rate defined as the proportion of subjects who do not require a platelet transfusion or any rescue procedure for bleeding after randomization and up to 7 days following an elective procedure. Based on clinical opinion and the published results of a similar compound in adults with thrombocytopenia associated with liver disease (ELEVATE study), the response rate in the placebo group is assumed to be 18%. With each baseline platelet count cohort, a sample size of 100 randomized subjects, 67 subjects for avatrombopag and 33 subjects for placebo, will have greater than 90% power to detect an absolute difference of 35% between the avatrombopag response rate and the placebo response rate assuming 18% response rate for placebo using Fisher's Exact tests with a 2-sided  $\alpha=0.05$ . (revised per Amendment 04) The hypothesized treatment group difference is based on platelet count changes found in the Phase 2 study (E5501-G000-202) and dose-response modeling using data from that study and others in the project development. Based on the baseline data in the Phase 2 study and assuming these are projected to be similar for this study, it is anticipated that this study will enroll roughly half of the total number of subjects in each of the 2 baseline platelet count cohorts to make the total sample size of 200 randomized subjects, 133 subjects for avatrombopag and 67 subjects for placebo. (revised per Amendment 04)

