### **Sample Size Rationale**

The proposed sample size is based on comparisons of the primary efficacy variable, with the response rate defined as the proportion of subjects who do not require a platelet transfusion or any rescue procedure for bleeding after randomization and up to 7 days following an elective procedure. Based on clinical opinion and the published results of a similar compound in adults with thrombocytopenia associated with liver disease (ELtrombopag EValuated for its Ability to overcome Thrombocytopenia and Enable procedures [ELEVATE] study), the response rate in the placebo group is assumed to be 18%. With each baseline platelet count cohort, a sample size of 100 randomized subjects, 67 subjects for avatrombopag and 33 subjects for placebo, will have greater than 90% power to detect an absolute difference of 35% between the avatrombopag response rate and the placebo response rate assuming 18% response rate for placebo using Fisher's Exact tests with a 2-sided  $\alpha=0.05$ . (revised per Amendment 04) The hypothesized treatment group difference is based on platelet count changes found in the Phase 2 study (E5501-G000-202) and dose-response modeling using data from that study and others in the project development. Based on the baseline data in the Phase 2 study and assuming these are projected to be similar for this study, it is anticipated that this study will enroll roughly half of the total number of subjects in each of the 2 baseline platelet count cohorts to make the total sample size of 200 randomized subjects, 133 subjects for avatrombopag and 67 subjects for placebo. (revised per Amendment 04)

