#### 9.1.2.3 Procedure Day (Visit 4)

This will occur 5 to 8 days after the last dose of study drug (on Study Day 10 to 13).

All Procedure Day assessments are to be completed prior to the procedure and include assessments shown in [Section 9.5.2.1 \(Table 5\)](#).

In addition, all subjects are required to return study drug and the dosing diary at this visit.

The elective procedure for those subjects whose preprocedural platelet count is  $>200 \times 10^9/L$  on Visit 4 (Procedure Day) may be delayed at the discretion of the investigator until platelet counts are below  $200 \times 10^9/L$ . All subjects whose platelet count exceeds  $200 \times 10^9/L$  will be required to have a Doppler assessment at Visit 5. For any subjects where the presence of a PVT is suspected, confirmation of diagnosis, via CT scan or MRI, should be performed and treatment for PVT initiated per local guidelines.

Permitted procedures and the risk of bleeding associated with each procedure are listed in [Table 1](#). It is planned that no fewer than 10% of subjects will be enrolled into the high risk group and no more than 60% of subjects in the low-risk group.

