### PRIMARY EFFICACY ANALYSIS

The primary efficacy variable is the proportion of subjects who do not require a platelet transfusion or any rescue procedure for bleeding after randomization and up to 7 days following an elective procedure.

The null hypothesis is that the proportion of subjects not requiring a platelet transfusion or any rescue procedure for bleeding after randomization and up to 7 days following an elective procedure is the same between the avatrombopag and placebo treatment groups. The corresponding alternative hypothesis is that the proportion of subjects not requiring a platelet transfusion or any rescue procedure for bleeding after randomization and up to 7 days following an elective procedure is not the same between avatrombopag and placebo. This hypothesis will be tested separately within each baseline platelet cohort.

The proportion of subjects not requiring a platelet transfusion or any rescue procedure for bleeding will be tested between the individual avatrombopag treatment group (40 or 60 mg) and matching placebo within each baseline platelet count cohort ( $<40 \times 10^9/L$  or from 40 to  $<50 \times 10^9/L$ ), each at a significance level of  $\alpha=0.05$ , using the generalized Cochran Mantel Haenszel (CMH) test adjusting for risk of bleeding associated with the elective procedure (low, moderate, or high based on Amendment 02 categorization).

- For subjects with platelet count  $<40 \times 10^9/L$  at baseline, the treatment comparison will be carried out between the 60 mg avatrombopag treatment group versus matching placebo.
- For subjects with platelet count from 40 to  $<50 \times 10^9/L$  at baseline, the treatment comparison will be carried out between the 40 mg avatrombopag treatment group versus matching placebo.

This study will be considered as positive if statistical significance is achieved for the primary efficacy endpoint for both baseline platelet count cohorts.

The 95% confidence interval (CI) for the proportion of subjects not requiring a platelet transfusion or any rescue procedure for bleeding will be calculated for each treatment group within each baseline platelet count cohort. In addition, the 95% CI for the difference between avatrombopag and matching placebo will be provided within each baseline platelet count cohort.

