Since the HCC status is included in the randomization stratification for safety purposes only, not for efficacy consideration, HCC will not be included in the CMH model for the primary efficacy analysis.

Subjects with missing information about the primary efficacy outcome due to early withdrawal or other reasons will be considered as having received a transfusion for the primary analysis.

The following analyses will be considered as sensitivity analyses:

- PP analysis: The same primary efficacy analyses described above will be repeated based on the PP analysis set.
- Observed case: The same primary efficacy analyses described above will be repeated based on observed data. Subjects with missing information about the primary efficacy outcome will be excluded from this analysis.
- Fisher's exact Test: The same primary efficacy analyses described above will be carried out using Fisher's exact test.
- Modified primary efficacy endpoint: Proportion of subjects who do not require a platelet transfusion after randomization and up to 7 days following an elective procedure. This efficacy endpoint will be analyzed using the same approach as primary efficacy analysis using FAS.

Additional sensitivity analyses may also be explored, if deemed appropriate.

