4 DETERMINATION OF SAMPLE SIZE

The proposed sample size was based on comparisons of the primary efficacy variable, with the response rate defined as the proportion of subjects who do not require a platelet transfusion or any rescue procedure for bleeding after randomization and up to 7 days following an elective procedure. Based on clinical opinion and the published results of a similar compound in adults with thrombocytopenia associated with liver disease (ELtrombopag EValuated for its Ability to overcome Thrombocytopenia and Enable procedures [ELEVATE] study [Afdahl, 2012])², the response rate in the placebo group is assumed to be 18%. Within each baseline platelet count cohort, a sample size of 100 randomized subjects, 67 subjects for avatrombopag and 33 subjects for placebo, would have greater than 90% power to detect an absolute difference of 35% between the avatrombopag response rate and the placebo response rate assuming 18% response rate for placebo using Fisher's Exact tests with a 2-sided $\alpha=0.05$. The hypothesized treatment group difference was based on platelet count changes found in the Phase 2 study (E5501-G000-202) and dose-response modeling using data from that study and others in the project development. Based on the baseline data in the Phase 2 study and assuming these were projected to be similar for this study, it was anticipated that this study would enroll roughly half of the total number of subjects in each of the 2 baseline platelet count cohorts to make the total sample size of 200 randomized subjects, 133 subjects for avatrombopag and 67 subjects for placebo.

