5.3.3 Multiple Comparisons/Multiplicity

The primary efficacy endpoint will be tested between the individual avatrombopag treatment group (40 or 60 mg) and matching placebo within each baseline platelet count cohort ($<40 \times 10^9/L$ or from 40 to $<50 \times 10^9/L$), each at a significance level of $\alpha=0.05$. The primary efficacy endpoint is considered positive only if the tests are statistically significant for both baseline platelet count cohorts to control the family-wise Type I error rate at a significance level of $\alpha=0.05$.

A sequential gatekeeping testing procedure will be used for the secondary efficacy endpoints to control the family-wise Type I error rate at a significance level of $\alpha=0.05$. The secondary efficacy endpoints will be analyzed if the primary efficacy endpoint is statistically significant for both baseline platelet count cohorts. The first secondary efficacy endpoint is tested first within each baseline platelet count cohort, each at a significance level of $\alpha=0.05$. Only if the first secondary efficacy endpoint is statistically significant for both baseline platelet count cohorts, the analysis of second secondary efficacy endpoint will proceed within each baseline platelet count cohort, each at a significance level of $\alpha=0.05$. No alpha adjustment is planned for other efficacy endpoints.

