5.4.1 Primary Efficacy Analyses

The primary efficacy variable is the proportion of subjects who do not require a platelet transfusion or any rescue procedure for bleeding after randomization and up to 7 days following an elective procedure.

The null hypothesis is that the proportion of subjects not requiring a platelet transfusion or any rescue procedure for bleeding after randomization and up to 7 days following an elective procedure is the same between the avatrombopag and placebo treatment groups. The corresponding alternative hypothesis is that the proportion of subjects not requiring a platelet transfusion or any rescue procedure for bleeding after randomization and up to 7 days following an elective procedure is not the same between avatrombopag and placebo. This hypothesis will be tested separately with each baseline platelet count cohort.

The proportion of subjects not requiring a platelet transfusion or any rescue procedure for bleeding will be tested between the individual avatrombopag treatment group (40 or 60mg) and matching placebo within each baseline platelet count cohort ($<40 \times 10^9/L$ or from 40 to $<50 \times 10^9/L$), each at a significance level of $\alpha=0.05$ using the generalized Cochran Mantel Haenszel (CMH) test adjusting for the risk of bleeding associated with the elective procedure (low, moderate, or high based on Amendment 02 categorization).

- For subjects with platelet count $<40 \times 10^9/L$ at baseline, the treatment comparison will be carried out between the 60 mg avatrombopag treatment group (Group A) versus matching placebo (Group B).
- For subjects with platelet count from 40 to $<50 \times 10^9/L$ at baseline, the treatment comparison will be carried out between the 40 mg avatrombopag treatment group (Group C) versus matching placebo (Group D).

This study will be considered as positive if statistical significance is achieved for primary efficacy endpoints for both baseline platelet count cohorts.

The 95% CI for the proportion of subjects not requiring a platelet transfusion or any rescue procedure for bleeding will be calculated for each treatment group within each baseline platelet count cohort. In addition, the 95% CI for the difference between avatrombopag and matching placebo will also be provided within each baseline platelet count cohort using normal approximation method.

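### Is N=200 inadequately supported because power is given per cohort and not for the rule that both cohorts must be significant?

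*Protocol*

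**What the plan says.** The power statement appears three times with the same content. Protocol 9.7.2 has "67 subjects for avatrombopag and 33 subjects for placebo, will have greater than 90% power to detect an absolute difference of 35" percentage points. The Protocol synopsis (Sample Size Rationale) has "will have greater than 90% power to detect an absolute difference of 35", and SAP section 4 has "would have greater than 90% power to detect an absolute difference of 35". All three assume 18% response on placebo and Fisher's exact test at two-sided 0.05. All three tie the statement to one baseline platelet cohort of 100 subjects. The total of 200 then comes from expecting about half the subjects in each cohort.

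The success rule is stated separately. Protocol 9.7.1.6 says "This study will be considered as positive if statistical significance is achieved for the primary efficacy endpoint for both baseline platelet count cohorts", and SAP 5.4.1 repeats it. SAP 5.3.3 says "The primary efficacy endpoint is considered positive only if the tests are statistically significant for both baseline platelet count cohorts" and makes this the gate to the secondary endpoints. The primary test is CMH, adjusted for bleeding risk.

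On missing outcomes, Protocol 9.7.1.6 says "Subjects with missing information about the primary efficacy outcome due to early withdrawal or other reasons will be considered as having received a transfusion".

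The Amendment 04 revision table gives the reason for reducing N from about 300 to about 200: after consultation with the FDA, enrolment was judged adequate. No power figure accompanies that reason.

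**The concern.** A reader who sees power above 90% next to a total of 200 could take it as the chance that the trial succeeds. It is the chance that one named cohort succeeds. Because both must succeed, the chance of a positive trial is lower, and the only figure in print is the more favourable one.

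The timing adds to the unease. Amendment 04 cut N by a third and revised this paragraph while the both-cohorts rule was already in force. If power for the actual rule had turned out poor, the reduction would have put the trial at risk without the documents showing it. Missing outcomes counted as failures, with no stated allowance in the sample size, would push the same way.

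**Working it through.** **Inputs (Protocol 9.7.2 and SAP 4).** Placebo 18%; avatrombopag 18% + 35% = 53%; 67 and 33 subjects per cohort; two-sided 0.05.

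**1. Reproduce the plan's figure.** Exact Fisher power is the sum, over all pairs (a, b), of Bin(a; 67, 0.53) × Bin(b; 33, 0.18), counting the pairs whose two-sided Fisher p is at most 0.05. The result is 0.9262, so the claim of more than 90% per cohort is right.

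**2. Power for both cohorts.** The cohorts contain different subjects and are randomized separately, so the two test results are independent. Joint power is the product of the cohort powers, provided that the 35-point effect holds in both.

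| Test | Per cohort | Both cohorts |
|---|---|---|
| Fisher exact, 67/33 | 0.9262 | 0.9262² = 0.858 |
| Mantel-Haenszel, one stratum, exact, 67/33 | 0.9412 | 0.9412² = 0.886 |
| CMH, three strata, equal rates, simulated | 0.942 | 0.942² = 0.887 |

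The stated totals of 133 and 67 imply one cohort of 67/33 and one of 66/34. Joint power is then 0.9262 × 0.9255 = 0.857 (Fisher) or 0.9412 × 0.9492 = 0.893 (Mantel-Haenszel).

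**3. How firm the CMH figure is.** The documents give limits on the risk mix ("no fewer than 10% of subjects will be enrolled into the high risk group and no more than 60% of subjects" in the low-risk group) but no response rates by stratum. The 0.887 therefore rests on an added assumption of equal rates. I took strata of 41/20/6 avatrombopag and 21/9/3 placebo subjects and chose low/moderate/high rates that keep the overall rates near 53% and 18%:

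- 58/48/36% versus 21/14/10%. The averages are (41×0.58 + 20×0.48 + 6×0.36)/67 = 53.0% and (21×0.21 + 9×0.14 + 3×0.10)/33 = 18.1%. Joint power is about 90%.
- 63/43/20% versus 24/10/2%. The averages are (41×0.63 + 20×0.43 + 6×0.20)/67 = 53.2% and (21×0.24 + 9×0.10 + 3×0.02)/33 = 18.2%. Joint power is about 92%.

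In the other direction, a continuity-corrected CMH test with equal rates gives about 83%. These settings are illustrations. Only the Fisher figure follows from the printed inputs alone.

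**4. Distance from 90%, if that were the joint target.** Each cohort would need √0.90 = 0.949. With 67/33, a 37-point difference gives this by Fisher (0.9488² = 0.900), and a 36-point difference is enough for Mantel-Haenszel (0.9517² = 0.906). Keeping 35 points and exact 2:1 allocation, the total needed is 2 × (72 + 36) = 216 by Fisher or 2 × (68 + 34) = 204 by Mantel-Haenszel, against the planned 200.

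**5. Missing outcomes.** The documents give no missing rate. Assume a fraction m missing in both arms, counted as failures and not already reflected in the 18% and 53%, so that both rates are multiplied by (1 − m). For m = 3, 5 and 10%, joint power is 83.8, 82.4 and 78.4% (Fisher) or 86.6, 85.1 and 81.0% (Mantel-Haenszel). If the planning rates already count missing outcomes as failures, none of this reduction applies. The documents do not say which.

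**6. Type I error.** Each cohort is tested at 0.05 and both must pass. The chance of a false positive trial is at most 0.05 when the drug works in only one cohort, and about 0.05² = 0.0025 when it works in neither. Leaving joint power unstated changes neither figure.

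**The case for a change.** The case for a change is that power should describe the event that makes the trial positive. On the plan's own sizing test the chance of missing that event is 1 − 0.858, about 14%, against 1 − 0.926, about 7%, for one cohort. The remedy would be one sentence, costing no patients and no analysis. If 86% is acceptable, there is no reason to leave it out.

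The facts in this argument stand: the joint figure is absent, it is lower than the printed one, and stating it would do no harm. What does not stand is that something in the plan is wrong without it. The sentence is tied to one cohort in all three places and is true as written. The documents promise no joint power, so 86% falls short of nothing they state. A reader who knows the success rule needs one multiplication to get it.

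Two stronger versions also fail. An unqualified 89% for CMH could not be printed as fact, because it depends on stratum rates that the plan does not give. A statement that the figures assume complete data could be false, because the origin of the 18% (clinical opinion and a published trial) leaves open whether missing outcomes were already counted as failures. It is also inaccurate to say that per-cohort power is the only support for N=200. It is the only numerical support, but the amendment also cites consultation with the FDA.

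**Conclusion.** No change is needed. The per-cohort statement is correct (92.6% against a claim of more than 90%) and correctly labelled. Power for significance in both cohorts is not stated. It is about 86% by Fisher's test on the protocol's own assumptions. By CMH without continuity correction it is about 89% with equal rates across risk strata, and about 90 to 92% in the two unequal-rate settings tried. All of these figures assume a 35-point effect in both cohorts, and they would be lower if missing outcomes are not already reflected in the planning rates.

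The gap to a joint 90%, a benchmark the documents do not set, equals one to two points of assumed effect, or 4 to 16 subjects in 200. Amendment 04 reduced N because enrolment was already judged adequate, so restating power would alter no recruitment decision. The tests, the error control and the reading of the results would be the same with or without the joint figure.

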## **9.7.3 Interim Analysis**

No interim efficacy analysis is planned, and therefore no adjustment of the *P*-value for the final efficacy analysis is needed. However, to protect subjects' safety, an independent DSMB will be established to monitor the ongoing safety data. Some of the safety parameters that DSMB will review will include variables that are also being assessed in this study for efficacy (eg, platelet count to ensure there are not too many subjects with a platelet count that exceeds  $200 \times 10^9/L$  and bleeding). The DSMB interim safety analysis will be performed by an independent statistician and governed by an external DSMB. To maintain the blinding and integrity of the

---

study, procedures will be implemented to ensure the DSMB and independent statistician have sole access to unblinded interim safety data.

Full details of the DSMB procedures, including primary responsibilities of the DSMB, its relationship with other study components, its membership, and its purpose and timings of its meetings, will be documented in a DSMB Charter. These details will also include procedures to ensure confidentiality and proper communication, the guidelines to be implemented by the DSMB, and an outline of the content of the closed reports (unblinded) and open reports (blinded) that will be provided to the DSMB.

